Study Protocol Cover Page

Study Title: Mindfulness-Based Stress Reduction to Improve Neuropsychological Functioning in Acquired Brain Injury

Clinical Trials ID: NCT03969563

Document date/IRB approval date: 10/31/2019

Treatment Protocol

We conducted six rounds of each class (see Table 2 for course topics and descriptions). To reduce variability, both courses had the same instructor - a trained and certified MBSR instructor with over 10 years of experience and a Master's degree in Education (emphasis on Curriculum and Instruction) - making her well-qualified to teach both classes. The instructor also received specialized training for teaching MBSR and other educational courses online. Both classes were further matched in terms of the length (2.5 hours/week), schedule (9-week class plus a day-long retreat), class size (7-10 participants), instructor, and amount of homework. All participants were also informed at the beginning of the course that their data would be excluded from the study if they missed more than three classes.

The MBSR class was the standardized program created by the University of Massachusetts, which includes an introductory session, 8 weeks of classes, and a retreat during the sixth week (Kabat-Zinn, 1990b). During the course, participants learned about mindfulness through practices such as body awareness, mindful movement, meditation, and informal mindfulness practices of daily life (e.g., eating, communicating, working, coping). The retreat included a review of class material, meditation and yoga practice, and a group lunch. Our study modified this program slightly by reducing the retreat day to four hours. And, given the population and the course modality, participants completed smaller movement and chair yoga exercises instead of the standard yoga practices. For homework, MBSR participants were assigned practices according to the standard MBSR curriculum, where they followed along to different meditation recordings (provided to them through a web link), engaged in mindful movement, and read from the course manual. The time spent engaging in mindfulness practices were then tracked using online homework logs.

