Our active intervention, the Brain Health class, was a modification of an existing VA education class for brain-injured individuals taught on the VA campus. It served as a robust active control because it matched the MBSR intervention in terms of instructor, time interacting with peers and the instructor, movement, schedule, and homework activities. The Brain Health class did not include any meditative/ mindfulness components, which we hypothesized would be the critical factor for how MBSR leads to improved health and cognition (Kabat-Zinn, 1990b).

Specifically, each class consisted of lectures with slides and videos (90 mins) and a group discussion (45 mins), during which time participants learned basic brain anatomy, how brain injuries can affect their cognition, and completed classes on the importance of topics such as sleep, nutrition, and social connection. To match the movement portion of the MBSR class, the Brain Health class also included simple chair exercises, such as stretching and reaching. The Brain Health retreat consisted of a review of class topics, short videos on brain topics, and a group lunch.

Measures

Study Implementation and Satisfaction. We measured study feasibility by examining rates of recruitment (i.e., the percentage of participants who agreed to take part in the study, relative to the total number of people we contacted) and retention (i.e., how many participants completed the program, attendance, homework engagement, and instructor-rated class engagement). Participants were also asked to complete an anonymous nine-item questionnaire created by the authors (see Table 3) to assess course satisfaction. Participants thus used a scale of 1 (very unsatisfied) to 5 (very satisfied) to answer questions such as, "How satisfied were you with the class?" and "How likely are you to continue to study and practice the skills you learned in this class?".

Mood, Well-Being, and Health. The Geriatric Depression Scale (Yesavage et al., 1982) was administered to measure subjective symptoms of depression in an older adult population. Participants indicated yes (1) or no (0) to questions such as, "*Do you feel happy most of the time?*" and "*Do you feel your situation is hopeless?*". The State-Trait Anxiety Inventory (Spielberger et al., 1983) measured current anxiety symptoms. Participants used a 1 (almost never) to 4 (almost always) scale to express how often they "feel content," and "feel calm."

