## **Data Analytic Approach**

Preliminary analyses examined potential class differences (i.e., MBSR, Brain Health) in participant demographics (i.e., sex, age, education). Variables that differed across groups were included as covariates when appropriate. For primary analyses, we examined measures collected at one timepoint (i.e., implementation, satisfaction), using a multivariate ANOVA (MANOVA) as an omnibus test for measures with multiple dependent variables. If post-hoc analyses were completed, Bonferroni adjusted pvalues were applied. Pairwise comparisons were examined with independent t-tests for continuous variables and Chi-square analyses for binary variables. For outcome variables collected at multiple timepoints (i.e., cognitive functioning, health and wellbeing measures), linear mixed effects models ("Ime4" package v. 1.1–21 in "R" v. 3.6.3) were used to examine each outcome. Class (MBSR, Brain Health) and time (preintervention, post-intervention, and six month follow-up) were entered as fixed effects, participants were entered as a random effect, and the outcome variable was entered as a dependent variable. Main effects of class and time, as well as the class x time interaction (reflecting intervention effects) were examined.

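### If allocation was random, modelling the pre-intervention score as a response usually costs power against a baseline-adjusted joint test, most at low to moderate correlation with a lasting effect

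*SAP*

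**What the plan says.** Under Data Analytic Approach, the SAP gives each outcome measured more than once its own linear mixed model. The terms are class and "time (preintervention, post-intervention, and six month follow-up) were entered as fixed effects, participants were entered as a random effect". The pre-intervention score is thus one of three levels of time. No random slope is described, so I read the participant effect as a random intercept. On testing, the SAP says: "Main effects of class and time, as well as the class x time interaction (reflecting intervention effects) were examined". With two classes and three times, the interaction has 2 numerator degrees of freedom.

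The covariate rule has two steps: "Preliminary analyses examined potential class differences (i.e., MBSR, Brain Health) in participant demographics (i.e., sex, age, education", and then "Variables that differed across groups were included as covariates when appropriate". The baseline value of the outcome is not named.

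The status of these outcomes is unclear. The SAP writes "For primary analyses, we examined measures collected at one timepoint (i.e., implementation, satisfaction", which attaches the word primary to other measures. The Protocol, however, says of the mindfulness component, "which we hypothesized would be the critical factor for how MBSR leads to improved health and cognition", and the interaction is the test of that hypothesis.

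Two statements under Treatment Protocol also matter: "We conducted six rounds of each class", with 7 to 10 people in each, and the warning to participants that "their data would be excluded from the study if they missed more than three classes".

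The text available for this review does not say how people were allocated. Part of the SAP was removed before review, so I treat this as unknown and not as a gap in the plan.

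**The concern.** Because the class effect is free at the pre-intervention visit, the complete-data interaction test compares the classes on change from baseline. Under random allocation the true baseline means are equal, so any observed baseline difference is noise. A change score subtracts all of that noise; a baseline-adjusted analysis subtracts only the part that predicts follow-up. The covariate rule does not recover the loss, because it names only sex, age and education and admits a variable only if it differs between classes.

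At stake is a lasting effect on cognition or wellbeing that the planned test could miss and the same data would show after adjustment.

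The attendance exclusion complicates the remedy. It operates after classes have started, so it can leave the analysed classes truly different at baseline. Change-based and adjusted estimates can then disagree.

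**Working it through.** The available text gives no sample size, power, alpha, effect size or correlation, so there is no figure of the plan's own to reproduce.

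**Inputs.** From the Protocol: 2 classes x 6 rounds x 7 to 10 people gives N = 84 to 120 before exclusions, or n = 42 to 60 per class. Assumed: SD 1, equal correlation rho between all visits, 5% level, complete data, no clustering, random allocation, and an effect of 0.4 SD at post that persists, halves or is gone by six months.

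**Formulas.** Let d1 and d2 be the class differences at post and six months, s = (d1+d2)/2 and t = (d1-d2)/2.

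- Planned test: F with 2 and 2(N-2) df, noncentrality (n/2)(2s²/3 + 2t²)/(1-rho).
- Adjusted joint test: F with 2 and N-4 df, noncentrality (n/2)(2s²/(1+2rho) + 2t²)/(1-rho).

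Only the term in the average effect s differs. The ratio (adjusted/planned) therefore runs from 1, when s = 0, to 3/(1+2rho), when t = 0. It rises as rho falls.

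**Worked case.** N=84, rho 0.5, d1 = d2 = 0.4, so s = 0.4 and t = 0. Planned: 21 x (2 x 0.16/3)/0.5 = 4.48. Adjusted: 21 x (2 x 0.16/2)/0.5 = 6.72. The ratio is 1.50. Power is 45.1% against 61.9%.

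**Power, planned vs adjusted (%).**

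| N | Effect (post, six months) | rho 0.1 | rho 0.5 | rho 0.7 | rho 0.8 | rho 0.9 |
|---|---|---|---|---|---|---|
| 84 | 0.4, 0.4 | 26.8 vs 58.3 | 45.1 vs 61.9 | 67.7 vs 77.0 | 85.2 vs 89.5 | 99.2 vs 99.4 |
| 84 | 0.4, 0.2 | 21.0 vs 39.9 | 35.0 vs 45.6 | 54.5 vs 61.4 | 73.2 vs 77.2 | 96.2 vs 96.7 |
| 84 | 0.4, 0 | 26.8 vs 35.0 | 45.1 vs 49.1 | 67.7 vs 69.6 | 85.2 vs 85.9 | 99.2 vs 99.1 |
| 120 | 0.4, 0.4 | 37.0 vs 75.4 | 60.8 vs 78.7 | 83.6 vs 90.8 | 95.4 vs 97.4 | 100 vs 100 |
| 120 | 0.4, 0 | 37.0 vs 48.3 | 60.8 vs 65.6 | 83.6 vs 85.4 | 95.4 vs 95.9 | 100 vs 100 |

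At N=84, rho 0.9 and post only, the noncentrality ratio is 1.018, and the drop in denominator df from 164 to 80 cancels it.

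**Simulation check.** N=84, rho 0.5, 0.4 SD at both follow-ups, 8,000 runs: 45.2% vs 61.2%. With no effect (50 per class, 4,000 runs, rho 0.3, 0.5 and 0.8), type I error was 4.7 to 5.6% across both tests.

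**Attendance exclusion.** At a given visit the change-based estimate subtracts the full baseline class difference B, and the adjusted one subtracts rho x B. They differ by (1-rho)B. For B = 0.2 SD this is 0.10, 0.06 and 0.04 SD at rho 0.5, 0.7 and 0.8. A simulation of 2,000,000 records had no true effect and excluded 15% per class, at random in one class and selectively in the other (logistic slope 1 per SD). Error in SD:

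| Exclusion depends on | rho | Change-based | Adjusted |
|---|---|---|---|
| Baseline score | 0.5 | 0.06 | 0.00 |
| Baseline score | 0.7 | 0.04 | 0.00 |
| Stable trait | 0.5 | 0.00 | 0.05 |
| Stable trait | 0.7 | 0.00 | 0.03 |

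Which estimate is biased depends on a mechanism that the documents do not describe.

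**The case against.** The strongest defence is that the planned model is coherent, keeps its error rate and does not need equal baseline means. That is a sensible property when allocation is not visible and people are excluded after classes start. This stands: the point is about efficiency, and it exists only if allocation was random.

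It can also be said that the percentages rest on assumed effects and correlations and ignore delivery in 12 class groups. This stands too. They compare two tests under the same assumptions and do not forecast this trial's power.

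Finally, the SAP is written in the past tense, so a change may come too late to be prespecified. That limits the label the new analysis may carry but does not remove its use.

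A reader might go further and infer that the planned test is biased, that the trial is underpowered, or that the adjusted model should always lead. The documents support none of these. Simulated type I error is near 5% for both tests, no design assumptions are given against which to judge power, and with the attendance exclusion in place either estimate can be the biased one.

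**Conclusion.** The point holds as a conditional improvement to a valid analysis. If allocation was random, the planned interaction test usually has less power than a baseline-adjusted joint test. At N=84 with 0.4 SD at both follow-ups, the gain from adjustment is 31.5 points at rho 0.1, 16.8 at 0.5, 9.3 at 0.7 and 4.3 at 0.8. With an effect at post only it is 4.0 points at 0.5, 0.7 at 0.8 and nil at 0.9. So the gain is large when correlation is low to moderate and the effect persists. It is small or nil when correlation is about 0.8 or more or, at moderate correlation, when the effect is gone by six months. It would be wrong to infer that only moderate correlation matters, since the gain is greatest at low correlation. Some gain also remains at rho 0.1 for an effect that does not last (8.2 points at N=84).

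These sizes assume equal correlations, complete data, no clustering and no exclusions.

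**What to change.** **If allocation was random:** model the post and six-month scores with class x time and baseline score x time, under an unstructured covariance (for example gls in nlme). Test the two class differences jointly on 2 df. In this model class x time alone asks only whether the effect changes between visits, so it must not be carried over as the test. Analyse everyone allocated who has data, without the attendance exclusion.

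**If the attendance exclusion is kept:** report the change-based and baseline-adjusted results side by side, without ranking them, and give the baseline class difference in the analysed set.

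**If allocation was not random:** keep the planned model.

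**If results are already known:** label the adjusted model as an additional analysis beside the planned one.

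The SAP should also say whether the repeatedly measured outcomes are primary.

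The cost is a few SAP sentences, a different R function and one more covariance parameter (3 instead of 2). The baseline score is already collected. People with poor attendance can be included only where their follow-up scores exist.

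### Both courses are taught in groups (12 groups of 7-10), but no outcome analysis allows for correlation within a taught group, so standard errors for class comparisons may be too small

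*SAP*

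**What the plan says.** The Protocol, under Treatment Protocol, states "We conducted six rounds of each class", with 7 to 10 people per class. It adds that "both courses had the same instructor" and that participants were told "their data would be excluded from the study if they missed more than three classes". Of the Brain Health course it says "it matched the MBSR intervention in terms of instructor, time interacting with peers and the instructor"; part of each of its sessions is a group discussion.

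The SAP, under Data Analytic Approach, fits linear mixed models to the outcomes measured three times. The fixed effects are class and time, and "participants were entered as a random effect, and the outcome variable was entered as a dependent variable". Class here has two levels, MBSR and Brain Health: it is the course, not the taught group. The class x time interaction is read as the intervention effect. Outcomes measured once are analysed by MANOVA, with independent t-tests or chi-square tests for pairwise comparisons. The only other terms are demographic covariates that differ between courses. The section mentions no term for round or taught group, no cluster-robust standard error and no group-level test.

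**The concern.** People in one taught group share weekly sessions, a retreat, peers and discussion. How one round went can move its members' outcomes together. Each course then rests on six groups, and the participants within a group are not fully independent observations. A model with a participant effect only sets that correlation to zero without saying so.

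At stake is whether a difference produced by one or two unusual groups could be reported as an effect of MBSR. As the plan stands, a reader cannot tell whether a class x time result depends on the omission.

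The baseline comparisons of sex, age and education come before any teaching and need no change.

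**Working it through.** **Inputs from the documents.** Six rounds x 2 courses = 12 taught groups. At 7-10 each, that is 84-120 participants if all groups were of that size. There are three visits, with participant as the only random effect. The plan has no sample-size or error-rate figure to reproduce.

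**Assumed, because not stated.** Two-sided 5%; ICC 0.01-0.10; an F test for class x time (the SAP names no test statistic or degrees of freedom); participant variance 0.6 and residual variance 0.4, so total outcome variance 1.

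**Single-timepoint t-tests, by formula.** With m per group, design effect D = 1 + (m - 1) x ICC and actual error = 2 x (1 - Phi(1.96/sqrt(D))).

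- m = 7, ICC 0.05: D = 1 + 6 x 0.05 = 1.30; 1.96/sqrt(1.30) = 1.72; error 8.6%. The unadjusted standard error is 1 - 1/sqrt(1.30) = 12.3% too small.
- m = 10, ICC 0.05: D = 1 + 9 x 0.05 = 1.45; 1.96/sqrt(1.45) = 1.63; error 10.4%. The standard error is 17.0% too small.
- The same formula gives 5.7-6.1% at ICC 0.01, 6.4-7.1% at 0.02 and 12-16% at 0.10.

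**Class x time, by simulation.** Six groups per course. The group effect is zero at baseline and equal at the two later visits. The ICC is that of the pre-post change: with group variance v, ICC = v/(v + 2 x 0.4). ICC 0.05 therefore means v = 0.05 x 0.8/0.95 = 0.042.

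| ICC of change | Type I error, 7-10 per group | Type I error, 5 per group |
|---|---|---|
| 0 | about 5% | about 5% |
| 0.01 | about 5.4-6.0% | 5.5% |
| 0.02 | 6-7% | 5.8% |
| 0.05 | 8-10% | 7.3% |
| 0.10 | 12-16% | 9.9% |

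The last column shows what happens if the attendance exclusion and dropout shrink the groups.

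**Dependence on the form of the group effect.** If it halves by six months, the class x time error at ICC 0.05 is 7.5-9.0% with 7-10 per group. If it is the same at all three visits (group variance 0.05), it cancels from class x time (4.8-4.9%), but the class main effect rejects in about 10-12%. If independent group effects of variance 0.05 arise at each later visit, the class x time error is 13-17%.

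**Group-level tests.** In the scenarios with a persistent group effect, the class x time F against group-by-time variation rejects in 4.7-5.9%. Two tests on the 12 group mean changes, at 0.025 each, reject in about 4.3-5.3% overall. Both are close to nominal.

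**The case against.** The strongest objection is that the harm is wholly conditional. No ICC is given. One instructor taught every group on matched schedules, which removes instructor differences as a source of correlation. At ICC 0.01-0.02 the inflation is about 1-2 points, and if group effects are stable the class x time test is unaffected. This stands, and it limits the weight of the point. It does not remove it, because one instructor does not remove the effect of particular peers or of how a given round went.

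A reader might infer that the planned class x time test is shown to be inflated, or that 8-16% is the expected error. The documents do not support either. Those figures need an ICC of 0.05-0.10 on the change, and they move with how the group effect is modelled. Only the omission of the term is certain.

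A second objection concerns reach. The SAP introduces its primary analyses with implementation and satisfaction measures. The satisfaction forms are anonymous, so they may not be linkable to a round, and no binary outcome is named for the chi-square test. This also stands. It leaves the longitudinal outcomes and those implementation measures that can be linked. The Protocol lists "how many participants completed the program, attendance, homework engagement, and instructor-rated class engagement"; attendance and the homework logs are not described as anonymous.

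Part of the SAP text was not available for review. Data Analytic Approach lists its model terms itself, so the reading does not rest on what is absent.

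**Conclusion.** The point holds in conditional form. The analysis ignores the 12 taught groups. If outcomes correlate within them, standard errors for class comparisons are too small: for class x time through group effects that change over time, and for the class main effect and single-timepoint tests through stable ones as well. The size runs from negligible to roughly a tripling of the nominal 5% at ICC 0.10 with 10 per group, and the low end is plausible here. This rests on the assumed ICC range, 5% two-sided level, F test and variance split.

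It should be fixed because the repair is cheap and lets readers judge. It is not evidence that any result is wrong.

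**What to change.** **Class x time.** Pre-specify one group-level test, chosen so that it does not depend on whether a variance is estimated as zero. There are two options:

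- the class x time F against group-by-time variation, with 2 and (12 - 2) x (3 - 1) = 20 df if balanced; or
- tests of the 12 group mean changes, pre to post and pre to six months, with 10 df each and at 0.025 each.

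A random group intercept alone does not protect class x time.

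**ICC.** Fit `y ~ class*time + (1|participant) + (1|group) + (1|group:time)` and report the ICC with its interval. Expect a singular fit in most datasets at low ICC: at least one group variance is estimated at zero in about 71-74% at ICC 0.02 and 55-63% at 0.05. This model should therefore describe the correlation, not carry the test.

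**Single-timepoint outcomes.** Where a continuous outcome can be linked to a round, test group means or add a random group intercept. If the planned MANOVA is kept, state that it ignores grouping. For anonymous forms that cannot be linked, state the limitation. Any binary outcome compared after teaching needs a cluster-adjusted test.

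**Timing.** The SAP is in the past tense. If the analysis is done, report all this as a sensitivity analysis labelled as added later.

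**Cost.** A few lines of code where round is recorded. At ICC 0, for a difference of 0.5 outcome SD, class x time power with 7-10 per group is about 69-84% with the F on 2 and 20 df. It is 68-83% for at least one of the two group-mean tests (50-67% for each). The planned analysis has 75-89%. These figures are for 0.5 SD of the outcome, which is 0.5/sqrt(0.8) = 0.56 SD of the change. Group mean changes also use only participants seen at both visits, which the mixed model does not require.
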